**Protocol:**

## PROTOCOL

Patients of ages 18 to 90 years old with ASA class I-IV undergoing elective lumbar interbody fusion (PLIF or TLIF) for degenerative disc disease (DDD) are considered eligible for inclusion in this study. Patients are screened for the inclusion/exclusion criteria below. Patients will enroll

in the study at the time of signing consent for surgery at their preoperative visit. Participation in the study has no bearing on their consent for surgery. After the patient signs consent at the preoperative visit, they will complete the baseline cognitive assessment (TICS-m, COWAT, TMT, BDI, 3D-CAM). Patients will have from the first visit until the day of surgery to withdraw from the study (2-6 weeks) and from the first visit to the preop visit to consent (1-4 weeks). Once patients are consented, they are considered enrolled. Patients can withdraw out of the study at any time prior to surgery. Once they withdraw, they will no longer be considered participants in the study. Patients will be randomized (blind randomization) using SPSS to placebo vs TXA. The primary surgeon, anesthesia care provider, investigator, and outcomes assessor will be blinded to the treatment and control arms. The intraoperative estimated blood loss in milliliters will be recorded routinely by the anesthesiologist participating in the case. All patients will be discharged to the neurosurgical or orthopedics wards postoperatively. Twice daily (~8am and ~4pm) a study member will administer the 3D-CAM or CAM-ICU delirium screening assessments to determine delirium status. Patients are followed until their second postoperative visit to clinic, approximately 3 months after the surgery. At the first visit, patients will be screened for any adverse events. At both the first and second visit postoperatively, the patients will complete the cognitive testing (TICS-m, COWAT, TMT, BDI, 3D-CAM).

Baseline Demographics/Data	
Age	Chronic Liver Disease
Sex	History of DVT, PE, TEE
Height	Oral anticoagulation (and reason for it)
Weight	Oral antiplatelet therapy (and reason for it)
BMI	Visual impairment
Smoking (Yes/No)	Number of levels fused
DM	Number of Interbody fused
Coronary Artery Disease	ASA classification
Peripheral Vascular Disease	OB/GYN: breast feeding, OCP or pregnant

**Chronic Kidney Disease**

**Chronic anemia (Hb<8)**

---

**Inclusion Criteria**

- 1) Age 18-90 years
- 2) ASIA anesthesia risk of I to IV
- 3) Patients undergoing posterior lumbar spinal fusion for DDD.
- 4) Patients have failed conservative management, which include PT/OT and/or injections.

**Exclusion:**

- 1) ASIA class V
- 2) Patient unable to consent
- 3) Patient with chronic kidney disease stage III or above: baseline plasma creatinine>1.5mg/dL
- 4) Patient with known liver failure
- 5) Patients on anticoagulation or dual antiplatelets (presence of vascular stents).
- 6) Patients with artificial valves.
- 7) Patients with allergy to TXA
- 8) Patients with platelet count < 150 000
- 9) Patients with PT>15s
- 10) Patients with APPT>38s
- 11) History of stroke or (an) unprovoked thromboembolic event(s).
- 12) History of intracranial bleeding,
- 13) Pregnancy
- 14) known defective color vision
- 15) history of venous or arterial thromboembolism or active thromboembolic disease
- 16) Patients with severe pulmonary or cardiac disease.
- 17) Patients who refuse transfusion of blood products
- 18) Patients with chronic anemia with Hg<8
- 19) Patients undergoing lumbar fusion for disease other than DDD (neoplasm)
- 20) Patients undergoing lumbar fusion by anterior or lateral approach.
- 21) Minimally invasive TLIF are excluded.
- 22) Emergent cases.
- 23) Women on hormonal contraception
- 24) Retinal vein or artery occlusion
- 25) Hypercoagulability
- 26) Seizure disorder
- 27) Current use of tretinoin
- 28) Current use of chlorpromazine
- 29) Breast feeding

Variables	Preop	Hospitalization	6-week f/u	3-month f/u
Demographics	X			
BHCG				
LFT *	X			
Coags (PTT/PT/INR)	X			
GFR	X	POD1		
SF Rand/ PROMIS	X		X	X
CBC	X	X		
Complications (DVT,PE,SSI,TE)		X	X	
Visual testing *	X	POD1		
New deficit		POD1		
	X	Intraop 1h postop (PACU) POD1,2,3		
Drain output/duration		X		
Blood Loss		X		
3D-CAM/CAM ICU*	X	X	X	X
TICS-m*	X		X	X

COWAT*	X	X	X
TMT*	X	X	X
BDI*	X	X	X

---

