**Primary Objective:**

1. To test the effect of TXA on the need for red blood cell (RBC) transfusion (intraoperatively and postoperatively) in patients undergoing lumbar spinal fusion compared to placebo (Normal Saline). This will be adjusted for number of levels to fuse, duration of surgery and patient's weight.
2. To test the effect of TXA on blood loss adjusted for weight, duration and number of level fused

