**Primary endpoints:**

1. The amount of RBC transfusion intraoperatively
2. The amount of RBC transfusion up to 7 days postoperatively
3. Measurement of intraoperative blood loss, postoperative blood loss, and total blood loss.

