#### **Indication for transfusion**

- Hb <7.0 mg/dl
- Anemic symptoms developed:
  - A decrease in blood pressure to <100 mmHg systolic,

- [tachycardia](#) greater than 100 beats/min
- Orthostatic hypotension , lightheadedness, Chest pain/palpitation, confusion (due to a low bp)
- Low urine output of <30 ml/h, after initial fluid challenge with 500 ml normal saline in patients with a hemoglobin level between 7.0 and 8.0 mg/dl.

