## Outcome assessment:

### 1) hemorrhage assessment:

- intraoperative [blood loss](#),
- [Total blood loss \(Calculated\)](#) and [Hidden Blood loss \(Calculated\)](#)
- [postoperative](#) drainage amount (per 8 h shift),
- days of drain in place, HGB level (before surgery and 1, 24h, 48 and 72 hours after surgery),
- [hematocrit](#) (HCT; same),
- [prothrombin time](#) (PT), PPT before,
- number of blood transfusions

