#### **Analysis of Primary End Point:**

The primary endpoint is the mean difference in total blood loss, intraoperative blood loss and postoperative blood loss. An ANOVA will be used to compare between the 2 groups. A type I error rate of 0.05 will be utilized. An exploratory GLM ANOVA will be used to test for interaction for the subgroups with number of level fused, BMI and duration of surgery.

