Cover Page for Statistical Analysis Plan

Sponsor-Investigator:	[name]
NCT Number:	NCT04272606
Unique Protocol ID:	201912099
Official Title:	Prospective, Randomized, Double Blind Study on the Effects of Tranexamic Acid on Intraoperative Blood Loss During Lumbar Spinal Fusion And Instrumentation
Date of Document:	05 December 2023

Statistical Analysis

All analyses will be conducted using R statistical software (version 4.3.1). Continuous variables will be summarized using medians and interquartile ranges and comparisons between groups will be done made using Wilcoxon rank sum or Kruskal-Wallis tests. Pairwise analyses within a group will be made using the Wilcoxon signed rank test. Categorical variables will be summarized using counts and percentages, and comparisons between groups will be performed using Pearson χ^2 test or Fisher exact test. Kendall's tau (τ) will be used as a non-parametric test of association between variables. For all analyses, the threshold for significance will be <0.05 without adjustment for multiple comparisons. Variables will be compared between groups by calculating standardized mean differences.

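### The transfusion objective does not adjust for preoperative haemoglobin, a plausible strong predictor that is already collected, and the SAP contains no adjusted model to hold it

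*Protocol*

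**What the plan says.** - **Entry.** Exclusion criterion 18 reads "Patients with chronic anemia with Hg<8". No upper limit is set, so entry Hb runs from 8 to normal.
- **Transfusion.** Under Indication for transfusion, Hb below 7.0 is an indication by itself. Low urine output after a fluid challenge is a second one, "in patients with a hemoglobin level between 7.0 and 8.0 mg/dl". The same list names low systolic pressure, tachycardia, orthostatic hypotension, chest pain and other symptoms. As printed, these carry no Hb value. (The printed unit is mg/dl; I read all Hb values as g/dL.)
- **Adjusters.** Primary Objective 1, on the need for RBC transfusion, states: "This will be adjusted for number of levels to fuse, duration of surgery and patient's weight". Hb is not among them.
- **Endpoints.** The first two primary endpoints are the amount of RBC transfused during surgery and "The amount of RBC transfusion up to 7 days postoperatively".
- **Protocol analysis.** Analysis of Primary End Point names only blood loss. There, "An ANOVA will be used to compare between the 2 groups", and an exploratory model will "test for interaction for the subgroups with number of level fused, BMI and duration of surgery". Hb is in neither.
- **SAP.** For continuous variables, "comparisons between groups will be done made using Wilcoxon rank sum or Kruskal-Wallis tests"; categorical variables get chi-square or Fisher tests. No covariate appears anywhere. Standardized mean differences between groups are planned, without naming the variables.
- **Randomisation.** Variable blocks, 1:1, with no stratification factor named.
- **Data.** Preoperative Hb is available: the hemorrhage assessment lists "HGB level (before surgery and 1, 24h, 48 and 72 hours after surgery", and the schedule has a preoperative CBC.

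**The concern.** A patient who starts at Hb 8 is 1 g/dL above the numeric trigger; one who starts at 14 is 7 g/dL above it. For the same blood loss, the first is more likely to be transfused. Starting Hb therefore plausibly explains part of the variation in RBC volume that has nothing to do with treatment.

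Leaving such a variable out of a randomised comparison has two costs. The residual variance is larger than it need be, so power is lost. And in a trial where the arms happen to differ in starting Hb, the unadjusted estimate is shifted in a known direction with nothing in the analysis to correct it. Neither balanced allocation nor adjustment guards against this here. The blood-volume side of the problem is partly covered by adjusting for weight, but the starting concentration is not.

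**Working it through.** **1. The plan's own figure.** The sample size section gives 40 per arm, 90% power, alpha 0.05, and meta-analytic differences of 681.81 ml (blood loss) and 234.61 ml (transfusion). The text available gives no SD, so 40 can be neither confirmed nor refuted. Solving backwards with SD = MD × √(n/2) / (z for alpha + z for power):
- Two-sided, transfusion: 234.61 × √20 / (1.960 + 1.282) = 323.7 ml.
- Two-sided, blood loss: 681.81 × √20 / 3.242 = 940.7 ml.
- One-sided: 358.5 ml and 1041.9 ml.

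Sidedness is not stated. I use 323.7 ml (two-sided).

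**2. Chance imbalance in Hb.** The 95% range of the difference in arm means is ±1.96 × SD × √(2/40) = ±0.438 × SD. For assumed Hb SDs of 1.0, 1.5 and 2.0 g/dL this is ±0.44, ±0.66 and ±0.88 g/dL.

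**3. Effect on the transfusion difference.** Let rho be the size of the correlation between preoperative Hb and RBC volume. It is not in the documents; I take 0.2 to 0.6. At the edge of the range in step 2 the shift is rho × 323.7 × 0.438, whatever the Hb SD. With Hb as a covariate the residual SD becomes 323.7 × √(1 − rho²). Power is by normal approximation.

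| rho | shift, ml | share of 234.61 ml | power at 40 per arm, adjusted (unadjusted 90%) | n per arm for 90%, adjusted |
|---|---|---|---|---|
| 0.2 | 28 | 12% | 91.1% | 39 |
| 0.3 | 43 | 18% | 92.5% | 37 |
| 0.4 | 57 | 24% | 94.3% | 34 |
| 0.5 | 71 | 30% | 96.3% | 30 |
| 0.6 | 85 | 36% | 98.2% | 26 |

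With the one-sided SD the shift runs from 0.2 × 358.5 × 0.438 = 31 ml to 0.6 × 358.5 × 0.438 = 94 ml, or 13% to 40%.

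**4. Simulation.** 40,000 trials per setting, 40 per arm, normal outcome, t-test against ANCOVA on Hb.
- No true effect, all trials: unadjusted type I error 0.051 (rho 0.3) and 0.050 (rho 0.5).
- No true effect, imbalance beyond 1.96 SE: unadjusted 10% to 12% (rho 0.3) and 17% (rho 0.5); ANCOVA 4% to 6%.
- No true effect, imbalance of about 1 SE: unadjusted 4% to 5%, so no inflation.
- True effect 234.61 ml, all trials: unadjusted power 89%; ANCOVA 92% (rho 0.3) and 95% (rho 0.5).
- True effect, TXA arm lower in Hb by more than 1.96 SE: unadjusted power 73% (rho 0.3) and 53% (rho 0.5); ANCOVA 91% and 94%.
- True effect, TXA arm lower by about 1 SE: unadjusted power about 82% and 81%.

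An imbalance beyond 1.96 SE occurs in 5% of trials, half of them in each direction.

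**The case against.** The strongest reply is that randomisation already deals with Hb. It does so on average: type I error over all trials stays near 5% without adjustment. A reader might infer that leaving Hb out makes the transfusion test invalid, or makes a false positive likely. The documents and the simulation do not support that. Inflation appears only in the rare, badly imbalanced trial.

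A reader might also compare individual headroom with the planned effect. Using the protocol's blood-volume and blood-loss formulas, with HCT taken as proportional to Hb, the loss needed to reach Hb 7 is volume × (Hb − 7) / ((Hb + 7)/2). For a man of 1.75 m and 85 kg (5.31 L) this is 0.71, 1.87, 2.79 and 3.54 L from Hb 8, 10, 12 and 14. For a woman of 1.62 m and 75 kg (4.18 L) it is 0.56, 1.48, 2.20 and 2.79 L. A 2 g/dL step thus changes headroom by 0.59 to 1.17 L, which exceeds 682 ml in five of six steps. But that compares two individuals. Chance acts on arm means. Near Hb 13 the slope is volume × 28/(Hb + 7)², about 0.37 and 0.29 L per g/dL, so the imbalances in step 2 of the working amount to roughly 0.13 to 0.33 L. That is well below 682 ml.

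Three further points stand. The symptom indications without an Hb value weaken the link between starting Hb and transfusion, so the documents do not show that starting Hb matters as much as blood lost. They give no Hb distribution, so how many patients will enter near 8 is unknown. And the planned standardized mean differences could reveal an imbalance, though they would not correct it.

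None of this restores the omitted covariate. It limits the size of the gain.

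**Conclusion.** The point holds as a matter of precision and of protection against chance imbalance, not of validity. The transfusion objective names three adjusters and omits a baseline variable that two of the trial's own transfusion indications depend on and that is already measured. The SAP goes further and provides no model even for the three that are named.

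The gain is modest if the correlation is 0.2 to 0.3 (power 91% to 92.5%, shift 12% to 18% of the effect at the edge of chance) and material at 0.5 or above (power 96% or more, shift 30% or more). These figures assume that the 40 per arm was derived from the transfusion difference with a two-sided test. They also assume a normal outcome analysed by t-test or ANCOVA. The SAP plans rank tests, and RBC volume may contain many zeros, so the figures are a guide to size and not a forecast.

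Criterion 18 supplies the range of starting Hb; it is not itself the fault, and nothing here calls for changing it.

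**What to change.** 1. In Primary Objective 1, add preoperative Hb, as a continuous variable, to the adjusters for RBC transfusion.
2. In the SAP, prespecify a covariate-adjusted analysis of both transfusion endpoints (intraoperative, and to day 7) that includes preoperative Hb. State the model form and whether it or the rank test is primary. If the sponsor wishes to stay close to the rank tests, a proportional-odds model is one option.
3. Name preoperative Hb among the variables compared by arm with standardized mean differences.

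Changing the objective alone would have no effect, because the SAP has no adjusted model to which a term could be added. Whether duration of surgery, which is measured after randomisation and is itself a secondary objective, belongs in that model is a separate question that this change does not settle.

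**Cost.** One adjusted model has to be written into the SAP. No patient, visit, blood test or procedure is added, and the sample size, criterion 18 and the transfusion indications stay unchanged.

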#### **Safety analysis:**

Adverse events occurring in the intraoperative period, immediate postoperative period and up to 4-8 weeks after the procedure will be recorded. We will collect specific adverse events that might be related to TXA treatment, including incidence of TTE, impaired renal function (plasma creatinine increase >20% of baseline level), and neurological complications, such as seizures and vision abnormalities. Adverse events apparently unrelated to use of the drug will also be recorded. The plasma creatinine will be obtained on POD1 and preoperatively. Severe adverse events are DVT and PE.

Sections including description of the anesthesia technique, transfusion requirements and blood loss, and venous thromboembolism prophylaxis are described in the Appendix. A comparison of the frequency and severity of adverse events occurring up to the 4-8-week follow-up period will be analyzed. Any SAE will be reported to the DSMB as they occur.

**Stopping rules or safety triggers for the study:** impairment in renal function and thromboembolic events will trigger a meeting of the DSMB to discuss the events and decide on the continuation of the trial. The study will automatically be placed on hold until the investigators and the DSMB can conduct a review of events. All AEs will be collected, recorded, and analyzed. Safety oversight for this study will be provided by both the DSMB and an independent Medical Safety Monitor. If the rate of thromboembolic events or impaired renal function crosses the literature threshold or the control group with 95% probability, the study will stop.

**Postoperative drain management:** The Hemovac drain is removed when the 8h output is <50 cc. The output is recorded for every 8 hour and charted.

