**Secondary endpoints:**

1. Safety analysis: thromboembolic events and worsening renal function in TXA vs placebo

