### **Sample Size Determination Based on Primary Endpoint (Blood loss and transfusion)**

We are planning a study of continuous response variable from independent control and experimental subjects with 1:1 allocation ratio. Primary calculations are based on the mean difference from a meta-analysis of RCT studies between patients who received TXA and those who received placebo. The amount of blood loss per patient significantly decreased with TXA with a mean difference (MD) of 681.81 ml (95% CI: 214.49 to 1149.12 ml). The pooled weighted MD for blood transfusion per patient between TXA group and placebo group is -234.61 ml (95% CI: -383.23 to -85.99 ml). However, there was significant heterogeneity within the selected studies. The TXA use could decreased 44% risk of blood transfusion compared with the placebo group with an OR of 0.56 (95% CI: 0.36 to 0.87). Based on the previous studies, we will need to study 40 experimental subjects and 40 control subjects to be able to reject the null hypothesis (i.e. the population means of the experimental and control groups are equal) with a probability of 0.9 (power = 90%) (Table 2). The Type I error probability associated with this test is 0.05. We will thus recruit 50 subjects per group and assume at least a 10% loss to follow-up. thrombosis complications and the use of TXA with an OR of 0.99 (95% CI: 0.06 to 16.07).

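### Renal safety is defined only as a creatinine rise above 20%, with no continuous comparison named; for small, roughly uniform shifts the yes/no test is much less sensitive than the data collected allow.

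*Protocol*

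**What the plan says.** The protocol's Secondary endpoints list a safety comparison of "thromboembolic events and worsening renal function in TXA vs placebo", without a metric. The Safety analysis section gives the only definition: "impaired renal function (plasma creatinine increase >20% of baseline level". The same section says "The plasma creatinine will be obtained on POD1 and preoperatively", and the schedule of assessments also lists GFR preoperatively and on POD1. The planned safety comparison is of events: "A comparison of the frequency and severity of adverse events occurring up to the 4-8-week follow-up period will be analyzed". The event rate also feeds the stopping rule: "If the rate of thromboembolic events or impaired renal function crosses the literature threshold or the control group with 95% probability, the study will stop".

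The protocol's Analysis of Secondary End Points covers length of stay, cost-effectiveness and the cognitive measures, and has no renal analysis. The section on sample size for secondary endpoints gives no renal power.

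The SAP names no endpoint. It has one general rule for continuous variables (medians, Wilcoxon rank sum). For the other type, it says "Categorical variables will be summarized using counts and percentages", compared by Pearson chi-square or Fisher exact test at 0.05, without multiplicity adjustment.

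**The concern.** An analyst who follows the only renal definition would count patients above the cut and compare two proportions. A patient at +19% then scores the same as one whose creatinine fell, although a paired change is available for each patient with both samples. If TXA moved creatinine by a modest amount in most patients, the count comparison would have little chance of showing it.

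Two things are at stake. A non-significant count could be taken as evidence of renal safety when it says little. And because no form of analysis is fixed, the choice between a count, a change, or no renal comparison at all could be made after the data are seen, in a plan that tests everything at 0.05 without adjustment.

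**Working it through.** **The plan's own figures.** No power or sample size is given for the renal endpoint. The trial size comes from the primary endpoint: 40 per arm, with "We will thus recruit 50 subjects per group and assume at least a 10% loss to follow-up". Since 40/0.90 = 44.4, 45 per arm would cover a 10% loss, and 50 × 0.90 = 45, so 50 is consistent with that text. I use 50 per arm and two-sided alpha 0.05 (the protocol does not state sidedness).

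**Assumptions, none of them in the documents.** The log ratio of POD1 to preoperative creatinine is normal with mean 0 in controls and SD 0.10 to 0.15. TXA adds a uniform shift *s* on the log scale. A log shift of 0.05 is a 5.1% rise (e^0.05 − 1), 0.07 is 7.3%, 0.10 is 10.5% and 0.15 is 16.2%.

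**Formulas.**
- Event rate: p = P(Z > (ln 1.2 − s)/SD), with ln 1.2 = 0.1823.
- Count comparison: exact binomial enumeration of all 2×2 tables, for Fisher and for uncorrected Pearson chi-square.
- Continuous comparison: two-sample t-test on the log ratio, noncentrality (s/SD) × √(50/2) = 5s/SD.

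**One case in full** (SD 0.12, s = 0.07). Control rate: 0.1823/0.12 = 1.519, so 6.4%. TXA rate: (0.1823 − 0.07)/0.12 = 0.936, so 17.5%. Fisher power is 27% and chi-square 42%. For the t-test, 5 × 0.07/0.12 = 2.92, giving 82%.

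| SD | log shift | control rate | TXA rate | Fisher | chi-square | t-test |
|---|---|---|---|---|---|---|
| 0.10 | 0.05 | 3.4% | 9.3% | 8.9% | 20.5% | 69.7% |
| 0.10 | 0.07 | 3.4% | 13.1% | 25.5% | 41.9% | 93.4% |
| 0.12 | 0.05 | 6.4% | 13.5% | 11.5% | 21.8% | 54.1% |
| 0.12 | 0.07 | 6.4% | 17.5% | 27.1% | 41.6% | 82.3% |
| 0.15 | 0.05 | 11.2% | 18.9% | 11.7% | 19.8% | 37.9% |
| 0.15 | 0.07 | 11.2% | 22.7% | 24.3% | 34.9% | 63.7% |
| 0.10 | 0.10 | 3.4% | 20.5% | 67.3% | 80.7% | 99.9% |
| 0.15 | 0.10 | 11.2% | 29.2% | 53.0% | 63.1% | 91.0% |
| 0.10 | 0.15 | 3.4% | 37.3% | 99.4% | 99.8% | >99.9% |
| 0.15 | 0.15 | 11.2% | 41.5% | 92.1% | 94.9% | 99.9% |

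**Sensitivity.**
- *Fewer patients.* At 45 per arm and log shifts of 0.05 to 0.07, Fisher has 7–26% and the t-test 35–91%.
- *Wider SD.* For a 10% rise (log shift 0.095), chi-square (Fisher) has 41% (33%) at SD 0.20 and 30% (23%) at SD 0.25; Wilcoxon on the log ratio has 64% and 46%.
- *Control mean not zero.* For a 10% rise and SD 0.10 to 0.25, chi-square power is 27–45% if controls fall by 0.05 on the log scale, and 31–90% if they rise by 0.05.
- *Rates alone.* A doubling from 5% to 10% has 16% power by chi-square and 6% by Fisher.

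**Non-uniform effect.** Suppose 20% of TXA patients rise by 40% and the rest do not change (SD 0.10). The control rate is 3.4%. The TXA rate is 0.8 × 3.4% + 0.2 × P(Z > (0.1823 − 0.3365)/0.10) = 2.7% + 0.2 × 93.8% = 21.5%. Simulated power is about 71% for Fisher, 84% for chi-square, 69% for the t-test and 40% for Wilcoxon. Here the cut does as well or better.

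**What the continuous estimate offers.** The 95% CI half-width on the log ratio is 1.96 × SD × √(2/50) = 0.392 × SD, or 0.039 to 0.059 for SD 0.10 to 0.15. The shift with 80% power is 0.560 × SD, or 0.056 to 0.084, which is a rise of 5.8% to 8.8%.

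**The case against.** A reader might infer that the cut would usually miss any renal effect in a trial of this size. The documents do not support that: they give no SD, control-arm change or expected shift, and with SD 0.10 to 0.15 a log shift of 0.10 is detected with 53–67% power by Fisher and 63–81% by chi-square. At 0.15 it is detected almost always.

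A reader might also infer that the SAP requires a count comparison. It does not: it names no endpoint, and its Wilcoxon rule for continuous variables could be applied to creatinine or GFR. The gap is one of specification. Quoting Fisher alone would also overstate the loss, because the SAP allows chi-square as well.

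The strongest objection concerns the shape of harm. The Safety analysis section treats renal impairment as an adverse event, which may strike a few patients hard. For that pattern the cut is a suitable test, so replacing it would lose something. This stands, and it is why the count comparison should stay.

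It is also fair that low power for a secondary safety endpoint is expected in a phase 2B trial of 100 patients, that no passage says a non-significant count will be read as safety, and that the documents do not say whether a 5–7% mean change on POD1 matters. Nor is the continuous test a cure: at SD 0.15 and a log shift of 0.05 it has only 38% power. These points limit the weight of the concern. They do not remove the case for naming a continuous comparison from samples already taken.

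**Conclusion.** The point holds in limited form. Worsening renal function is a between-arm secondary endpoint with one yes/no definition, both creatinine values are collected, and no continuous comparison is named. For small, roughly uniform shifts the yes/no comparison is much less sensitive: about 9–27% (Fisher) or 20–42% (chi-square) against 38–93%, at 50 per arm with log shifts of 0.05 to 0.07. These figures rest on an assumed SD of 0.10 to 0.15 and no mean change in controls. They do not extend to log shifts of 0.10 or more at those SDs, or to harm concentrated in a minority. This is a secondary safety endpoint, and the primary conclusion is not affected.

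**What to change.** Keep the between-arm comparison of rises above 20%, and leave its use in the DSMB trigger unchanged. Add to the SAP one prespecified analysis: an ANCOVA of log POD1 creatinine on arm and log preoperative creatinine, reporting the TXA-to-placebo ratio of geometric means with a 95% CI. Name both analyses as the renal safety comparison. State that a non-significant count comparison alone does not establish renal safety, and that the interval should be read for the size of shift it excludes.

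The cost is a few sentences in the SAP, with no new samples or visits. The downside is one more secondary safety analysis in a plan that makes no multiplicity adjustment, so the emphasis should be on the estimate and interval rather than on a p-value.

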### **Venous thromboembolism prophylaxis**

Patients received antithrombotic prophylaxis according to the institutional guidelines and protocols of each participating service and the individual risk estimated by the investigator. The study protocol includes evaluation of the probability that a patient would experience venous thromboembolism (VTE) using the Wells clinical prediction guide for deep venous thrombosis (DVT) and pulmonary embolism (PE) or the Geneva criteria for PE. DVTs are diagnosed by using US and PEs by using CTA. Clinically and radiologically confirmed DVT or PE are considered severe adverse events. LWMH or USQH were used after 24h of the procedure (adjusted to weight and renal function). Patients are mobilized as early as possible with Physical and occupational therapy.

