### **Study design:**

**Measures to minimize bias: randomization and blinding:** Randomized block design with variable block sizes will be used to randomize subjects to the 2 groups with a 1:1 ratio. Randomization will be generated by a randomization coding software (SAS Version 9.4). Randomization schema will be distributed to the pharmacy and sequence numbers will be identified to match patient enrollment. We will use triple masking: Concealment of randomization, blinding of treatment (placebo and TXA are indiscernible) and blinding of data analysis. Unmasking will be performed at the end of the trial. We will allow for unplanned masking in case of severe adverse events by the DSMB. (See Adverse events section).

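### The only stated definition of a severe adverse event names DVT and PE, so a seizure, or a visual loss or death that is not thromboembolic, has no stated expedited route to the DSMB and does not meet the stated unmasking condition

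*Protocol*

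**What the plan says.** Four places in the protocol bear on the point.

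- **Safety analysis, definition.** After listing adverse events that might be related to TXA (thromboembolic events, impaired renal function, and "neurological complications, such as seizures and vision abnormalities"), the section states "Severe adverse events are DVT and PE". It goes on: "Any SAE will be reported to the DSMB as they occur". The abbreviation SAE is not expanded anywhere.
- **Safety analysis, stopping rules.** Here "impairment in renal function and thromboembolic events will trigger a meeting of the DSMB", and the study is placed on hold pending review. The sentence on stopping the study refers to the same two categories. The section also says that all adverse events are recorded and analyzed, and that oversight is shared by the DSMB and an independent Medical Safety Monitor.
- **Venous thromboembolism prophylaxis.** "Clinically and radiologically confirmed DVT or PE are considered severe adverse events".
- **Study design, randomization and blinding.** "Unmasking will be performed at the end of the trial", with one exception: "We will allow for unplanned masking in case of severe adverse events by the DSMB". The context shows that unplanned *un*masking is meant. The sentence is followed by a pointer to an adverse events section.

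The SAP contains no safety definitions.

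**The concern.** A seriousness definition decides which events are escalated. Here the only definition given is a list of two venous diagnoses, not a set of criteria such as death, threat to life or lasting disability. Death is not mentioned as a safety event in the supplied text.

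This sits badly with the protocol's own view of where harm may arise. It names seizures and vision abnormalities as possible effects of the drug. It excludes patients with seizure disorder, retinal vessel occlusion or defective color vision, and it schedules visual testing before surgery and on the first postoperative day. The plan therefore looks for these harms but states no rapid route for them once found.

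At stake are how soon the DSMB learns of a grave event that is not thromboembolic, and whether it has clear authority to learn the patient's allocation. Safety is a secondary objective of the trial, so the classification also matters for reporting.

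**Working it through.** No arithmetic decides this. The check is to trace each kind of event through the rules as written.

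**Rules**
1. Severe class = DVT, PE (Safety analysis; venous thromboembolism prophylaxis).
2. Reporting to the DSMB as events occur = SAEs (Safety analysis). The only term in the protocol that SAE can abbreviate is severe adverse event, so rule 2 is read through rule 1.
3. DSMB meeting and hold = renal impairment, thromboembolic events (Safety analysis, stopping rules).
4. Unmasking before the end of the trial = severe adverse events (Study design), hence rule 1 again.

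**Result for each event**

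| Event | In severe class | Reported as it occurs | DSMB meeting and hold | Unmasking condition met |
|---|---|---|---|---|
| Confirmed DVT or PE | yes | yes | yes | yes |
| Arterial thromboembolic event | no | not under rule 2 | yes | no |
| Renal impairment (creatinine up more than 20%) | no | not under rule 2 | yes | no |
| Seizure | no | no | no | no |
| Visual loss, not thromboembolic | no | no | no | no |
| Death, not thromboembolic and without renal impairment | no | no | no | no |

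Of the four TXA-related categories named in Safety analysis, thromboembolism and renal impairment have a stated route to the DSMB. Seizure and vision abnormality have none, unless the visual event is itself thromboembolic.

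The ordering that results is odd. As an illustration, a creatinine rise from 1.0 to 1.21 mg/dL is (1.21 − 1.0)/1.0 = 21%. That exceeds the 20% limit, so it is a trigger for a DSMB meeting and a hold. A postoperative seizure is not.

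**Is the list closed?** The defining sentence has no opening word such as *including*. The same paragraph does use such words for the TXA-related events, so the authors marked a list as open when they meant one. The sentence in the prophylaxis section is weaker evidence: it says that these two diagnoses qualify, which fits an open or a closed list. No other supplied text widens the class.

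**The case against.** The strongest reply is that the list need not be exhaustive. The defining sentence follows a list of TXA-related events and may only say which of those count as severe. SAE may have been meant as *serious* adverse event, which would ordinarily include death, and the word *any* fits poorly with a list of two. The pointer to an adverse events section may lead to a fuller definition that was not supplied. These points stand as reasons for moderate confidence. They do not remove the defect: a broader meaning is nowhere stated, and the unmasking sentence says *severe* in full. The Appendix is also unlikely to help, since the topics listed for it are anesthesia technique, transfusion and blood loss, and thromboembolism prophylaxis. A wider definition elsewhere would still have to be reconciled with the sentence in Safety analysis.

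It is also true that all adverse events are recorded and that a Medical Safety Monitor shares oversight. This answers any charge that events go uncollected. It does not supply a timetable or route, because none is described for the Monitor.

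Three stronger readings are tempting, and the documents do not support them:

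- *No death or visual loss would reach the DSMB promptly.* A fatal PE is in the severe class, and any thromboembolic death or visual loss falls under the hold trigger.
- *The DSMB is barred from unmasking for other events.* The sentence is permissive. It states one condition and does not forbid others.
- *The between-arm comparison of severity would recognise only two diagnoses.* The protocol plans to compare frequency and severity of adverse events, but does not say that severity is graded by this class.

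**Conclusion.** The concern holds in a limited form. As written, a seizure, or a visual loss or death that is not thromboembolic, is recorded under general oversight but has no stated expedited route to the DSMB and does not meet the stated condition for unmasking. An arterial thromboembolic event brings a DSMB hold but lies outside the class for which unmasking is provided. In extent, two of the four named TXA-related categories lack a route, as does death that is neither thromboembolic nor accompanied by renal impairment.

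This rests on three assumptions: SAE abbreviates severe adverse event, the two-item list is complete, and no fuller definition exists in text that was not supplied. Confidence is moderate for that reason. The documents give no expected rates for seizure, visual loss or death, so the number of patients affected cannot be estimated. With 50 recruited per group it may be small. Staff may well report a death whatever the text says, but a safety rule should not depend on that. The change should be made; it does not affect the efficacy analysis.

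**What to change.** In Safety analysis, replace the defining sentence with an SAE definition based on seriousness: death, a life-threatening event, new or medically indicated prolonged hospitalization, persistent disability, or another medically important event. State that DVT, PE, arterial thromboembolic events, seizure and visual loss are reported to the DSMB as they occur. Use the same expanded term in Safety analysis, in the prophylaxis section and in the unmasking sentence. Correct *masking* to *unmasking* there, and make the pointer name a section that exists. Leave each unmasking decision to the DSMB's judgement, so that a wider definition does not make unmasking automatic.

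The hospitalization criterion needs its medical qualifier. Analysis of Secondary End Points says that actual discharge depends on insurance and facility availability, and delays of that kind should not count as serious events.

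The cost is one protocol paragraph, a few more DSMB reports and possibly a few more individual unmaskings in a trial that relies on masking. All adverse events are already collected, so no new data are needed. If enrolment is over, the same definition can still be used to classify the recorded events for the safety report.
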